CLINICAL STUDY PROTOCOL

APIXABAN FOR THE TREATMENT OF VENOUS THROMBOEMBOLISM IN PATIENTS WITH CANCER: A PROSPECTIVE RANDOMIZED OPEN BLINDED END-POINT (PROBE) STUDY - THE CARAVAGGIO STUDY

IND/EUDRACT NUMBER 2016-003093-40

Principal investigator & study chairman:
[name]

Internal and Cardiovascular Medicine and Stroke Unit

University of Perugia, Perugia, Italy

[contact]

Promoter:

Fondazione FADOI Italian Federation of Hospital Internists)

[name]

Rome, Italy

Protocol number: FADOI 03.2016

FINAL Version 3.0: May 22nd, 2018

SYNOPSIS

EudraCT/IND Number:	2016-003093-40
Protocol Number:	FADOI 03.2016
Investigational Product:	Apixaban (BMS-562247-01)
Study Title:	Apixaban for the treatment of venous thromboembolism in patients with cancer: a prospective randomized open blinded end-point (PROBE) study - the Caravaggio study
Short Title:	Apixaban for venous thromboembolism (VTE) in cancer patients
Study Phase:	Phase IIIb trial
Indication Under Investigation:	Apixaban for venous thromboembolism in cancer patients
Study Aim:	The aim of this study is to assess whether oral apixaban is non-inferior to the subcutaneous low molecular weight (LMWH) dalteparin for the treatment of newly diagnosed proximal deep vein thrombosis (DVT) and/or pulmonary embolism (PE) in patients with cancer.
Study Design:	This is a multinational, prospective, randomized, open-label, blinded end-point (PROBE), non-inferiority study.
Study population:	Inclusion criteria:
	 Consecutive patients with a newly diagnosed, objectively confirmed: symptomatic or unsuspected, proximal lower-limb DVT or symptomatic PE or unsuspected PE in a segmental or more proximal pulmonary artery.
	 2) Any type of cancer (other than basal-cell or squamous-cell carcinoma of the skin, primary brain tumor or known intracerebral metastases and acute leukemia) that meets at least one of the following: Active cancer defined as diagnosis of cancer within six months before the study inclusion, or receiving treatment for cancer at the time of inclusion or any treatment for

Caravaggio Study Protocol FINAL Version 3.0, May 22nd 2018

- cancer during 6 months prior to randomization, or recurrent locally advanced or metastatic cancer.
- Cancer diagnosed within 2 years before the study inclusion (history of cancer).
- 3) Signed and dated informed consent, available before the start of any specific trial procedure.

Exclusion criteria:

Patients are ineligible for the study in case of:

- 1) age <18 years
- 2) ECOG Performance Status III or IV;
- 3) life expectancy of less than 6 months;

related to anticoagulant treatment:

- 4) administration of therapeutic doses of LMWH, fondaparinux, or unfractionated heparin (UFH) for more than 72 hours before randomization;
- 5) 3 or more doses of a vitamin K antagonist before randomization;
- 6) thrombectomy, vena cava filter insertion, or thrombolysis used to manage the index episode;
- 7) indication for anticoagulant treatment for a disease other than the index VTE episode;
- 8) concomitant use of strong inhibitors or inducers of both cytochrome P-450 3A4 and P-Glycoprotein (see Appendix 1);

related to bleeding risk:

- 9) concomitant thienopyridine therapy (clopidogrel, prasugrel, or ticagrelor) or aspirin over 165 mg daily or dual antiplatelet therapy;
- 10) active bleeding or high risk of bleeding contraindicating anticoagulant treatment
- 11) recent (in the last 1 month prior to randomization) brain, spinal or ophthalmic surgery;

- 12) hemoglobin level lower than 8 g/dL (5.0 mmol/L) or platelet count <75x10⁹/L or history of heparin-induced thrombocytopenia;
- 13) creatinine clearance < 30 ml /min based on the Cockcroft Gault equation;
- 14) acute hepatitis, chronic active hepatitis, liver cirrhosis; or an alanine aminotransferase level 3 times or more and/or bilirubin level 2 times or more the upper limit of the normal range;
- 15) uncontrolled hypertension (systolic BP> 180 mm Hg or diastolic BP > 100 mm Hg despite antihypertensive treatment);

standard criteria:

- 16) bacterial endocarditis;
- 17) hypersensitivity to the study drugs or to any of their excipients;
- 18) Patient's participation in other pharmaco-therapeutic program with an experimental therapy that is known to affect the coagulation system.
- 19) women of childbearing potential (WOCBP) who do not practice a medically accepted highly effective contraception during the trial and one month beyond. Highly effective contraception methods are:
 - a. combined (estrogen and progestogen containing) hormonal contraception associated with inhibition of ovulation
 - b. progestogen-only hormonal contraception associated with inhibition of ovulation
 - c. intrauterine device (IUD)
 - d. intrauterine hormone-releasing system (IUS)
 - e. bilateral tubal occlusion
 - f. vasectomized partner
 - g. sexual abstinence;
- 20) pregnancy or breast feeding
- 21) any condition that, as judged by the investigator, would place the subject at increased risk of harm if he/she participated in the study.

Efficacy Study Outcomes:

Primary efficacy outcome: objectively confirmed recurrent VTE occurring during the study treatment period, that means the composite of:

- proximal DVT of the lower limbs (symptomatic or unsuspected)
- DVT of the upper limb (symptomatic)
- PE (symptomatic or unsuspected)

Secondary efficacy outcomes:

- the individual components of the primary efficacy outcome;
- symptomatic recurrence of VTE;
- all cause death;
- the composite of primary efficacy outcome plus major bleeding;
- the composite of primary efficacy outcome plus major bleeding plus all cause death;
- the composite of primary efficacy outcome plus all cause death:
- any major cardiovascular event, fatal or non-fatal (including acute myocardial infarction or ischemic stroke);
- all venous thromboembolic events (including splanchnic vein thrombosis and cerebral vein thrombosis):
- Quality of life (QoL) according to Anti-Clot Treatment Scale (ACTS) (see Appendix 2)

Safety Study Outcomes:

Primary safety outcome is major bleeding, defined (as per ISTH guidelines), as acute clinically overt bleeding associated with one or more of the following:

- decrease in hemoglobin of 2 g/dl (1.2 mmol/L) or more;
- transfusion of 2 or more units of packed red blood cells;

- bleeding that occurs in at least one critical site [intracranial, intra-spinal, intraocular (within the corpus of the eye; thus, a conjunctival bleed is not an intraocular bleed), pericardial, intraarticular, intramuscular with compartment syndrome, or retroperitoneal];
- bleeding that is fatal;
- bleeding that necessitates acute surgical intervention

Secondary safety outcomes include:

- Clinically relevant non-major bleeding event defined as acute clinically overt bleeding that does not meet the criteria for major and consists of:
 - any bleeding compromising hemodynamics;
 - spontaneous hematoma larger than 25 cm², or 100 cm² if there was a traumatic cause:
 - intramuscular hematoma documented by ultrasonography;
 - epistaxis or gingival bleeding requiring tamponade or other medical intervention or bleeding from venipuncture for >5 minutes:
 - hematuria that was macroscopic and was spontaneous or lasted for more than 24 hours after invasive procedures;
 - hemoptysis, hematemesis or spontaneous rectal bleeding requiring endoscopy or other medical intervention;
 - or any other bleeding considered to have clinical consequences for a patient such as medical intervention, the need for unscheduled contact (visit or telephone call) with a physician, or temporary cessation of a study drug, or associated with pain or impairment of activities of daily life.
- Clinically relevant bleeding defined as the composite of major and clinically relevant non-major bleeding
- Permanent early discontinuation of study drug due to safety reasons.

Study treatments and visits:

Patients will be randomized on a 1:1 basis (permuted blocks of four) to receive either apixaban or dalteparin in an open-label fashion.

Apixaban group: orally administered, at the dose of 10 mg bid for 7 days, followed by 5 mg bid (total period of treatment: six months)

Dalteparin group: subcutaneously administered, at a dose of 200 IU/kg SC o.i.d for 1 month. Thereafter, dalteparin will be administered at a

Caravaggio Study Protocol FINAL Version 3.0, May 22nd 2018

dose of 150 IU/kg o.i.d. for 5 months (total period of treatment: six months). The maximum daily dose allowed for dalteparin is 18,000IU.

Randomization will be centralized and stratified by:

- 1) symptomatic vs. unsuspected VTE
- 2) active cancer vs. history of cancer

Apixaban 5mg will be supplied by the Promoter as film-coated tablets.

Dalteparin will be supplied by the Promoter as single-use pre-filled syringes.

The study requires the following scheduled visits: at enrollment, at 4 weeks, at 3 months, at 6 months, at the end of study treatment whenever it occurs, and at 7 months from randomization.

Additional visits will be performed if new symptoms and/or signs of VTE or major bleeding develop. A clinical examination and objective tests will be performed if the patient develops symptoms or signs suggestive of recurrent VTE.

Planned Sample Size:

The study has been designed to test the hypothesis that apixaban would be non-inferior to dalteparin with respect to the primary efficacy outcome.

The criteria for non-inferiority require that the upper limit of the two-sided 95% confidence interval of the Hazard ratio is below the prespecified margin of 2.00.

With the use of an estimated incidence of the primary efficacy outcome of 7% at 6 months with dalteparin and an upper non-inferiority margin of 2.00 for the hazard ratio, we calculated that we would need to enroll 934 completer patients for the study to have 80% power to show the non-inferiority of apixaban, at a one-sided alpha level of 0.025. This sample will be increased to 1168 patients to account for up to 20% lost in total patient-years. This estimate is consistent with a drop-out rate of 40% assuming patients discontinued uniformly during the follow-up (mean discontinuation time equal to 3 months)

Statistical Analysis:

Analysis of the Primary Study Outcome

The primary efficacy data set will consist of all randomized subjects who received at least one dose of the study drugs (modified intent-to treat population) with a non-missing primary outcome. Subjects will be categorized to the group to which they were assigned at randomization, regardless of the treatment actually received.

Caravaggio Study Protocol FINAL Version 3.0, May 22nd 2018

The secondary efficacy data sets will consist of a) all randomized subjects (intent-to treat population) and b) the per-protocol population (defined in the SAP).

The safety data set will consist of all treated subjects (randomized subjects who received at least one dose of study drug).

The primary efficacy variable, i.e. the time from randomization to the first recurrent thromboembolic event, will be analyzed after adjusting estimates for the competing risk of death unrelated to VTE.

The evaluation of the primary objective will be done by considering the time from randomization to the first recurrent thromboembolic event (event of interest) or to the occurrence of death unrelated to VTE (nuisance/competing event) or to the last follow-up if neither a recurrent thromboembolic event nor a competing event occurred within the intended 6-month study treatment period (censored time).

Analyses of the primary efficacy endpoint will be performed using the modified intent-to-treat principle, the intent-to treat principle and the per protocol principle. The modified intent-to-treat and the intent-to-treat analyses of the primary endpoint will include endpoints that occur at any time from randomization until the end of their originally intended treatment period regardless of whether subjects were receiving study medication.

A per protocol analysis of the primary endpoint will include endpoints that occur in patients who complete the study fully compliant with the protocol and without any major violation or deviation (defined in the SAP).

For the secondary efficacy outcomes, analyses will be performed using the primary efficacy data set.

The apixaban-to-comparator Hazard Ratio adjusted for the competing risk of death unrelated to VTE will be computed with associated two-sided 95% Confidence Interval by resorting to the Fine & Gray regression model (Fine and Gray, 1999) using treatment group and center as dummy covariates.

Apixaban will be considered non-inferior to the comparator dalteparin if the upper two-sided 95% confidence limit of hazard ratio is < 2.00. Superiority of apixaban vs. dalteparin will be tested as a secondary analysis of the primary endpoint, only after non-inferiority has been demonstrated for the experimental treatment group (apixaban) relative to the standard treatment group (dalteparin). According to CPMP/EWP/482/99 document entitled: "Points to consider on switching between superiority and non-inferiority", switching the apixaban vs. dalteparin contrast from the non-inferiority objective to the superiority objective is feasible because the trial is properly designed in accordance to the strict requirements of a non-inferiority trial.

Caravaggio Study Protocol FINAL Version 3.0, May 22nd 2018

	For the purpose of safety analyses, subjects will be categorized to the group to which they were assigned at randomization unless incorrect study treatment was received throughout the study, in which case the subject will be categorized according to the treatment received. All safety analyses will be conducted on the safety population. The term "treatment period" refers to the period between the first administration of study drug and 48 hours after the last administration of study drug. This period will be the basis for the summaries of safety.
Study Sites and Location:	Approximately 140 study sites in 11 countries are planned to enroll patients in this study

TABLE OF CONTENTS

SYNOPSIS	2
1. LIST OF ABBREVIATIONS	12

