From the timing context point of view, our patient population is presumed to be closer to that of the CATCH study (published in 2015) than to the CLOT study (published in 2003). So it is plausible that patients enrolled in the Caravaggio study will receive less thrombogenic anticancer chemotherapy and improved disease management, as well as they will have less frequently a metastatic disease, due to an earlier diagnosis (screening improvement), like in the CATCH trial.

As a further support to our study hypothesis, the ONCENOX trial, published in 2006, compared Enoxaparin (1.0 mg/kg bid for 5 days + warfarin for 6 months) vs Enoxaparin (1.0 mg/kg bid for 5 days followed by Enoxaparin 1.0 mg/kg od) (low dose – LD) with Enoxaparin (1.5 mg/kg od (high dose - HD) for 6 months) (13). The study was small with limited statistical power, and recurrent VTE was only a secondary objective. However, the rate of this endpoint was 6.9% with the LD and 6.3% with the HD of enoxaparin, therefore comparable to that observed in the CATCH trial.

Recurrence rate for apixaban treated arm

In a post hoc analysis of the Amplify study, 169 patients (3.1%) had active cancer at baseline and 365 (6.8%) had a history of cancer without active cancer at baseline. Among patients with active cancer, recurrent VTE occurred in 3.7% and 6.4% of evaluable patients in the apixaban and enoxaparin/warfarin groups, respectively (relative risk 0.56, 95% confidence interval 0.13-2.37). Among patients with a history of cancer, recurrent VTE occurred in 1.1% and 6.3% of evaluable patients in the apixaban and enoxaparin/warfarin groups, respectively (relative risk 0.17, 95% confidence interval 0.04-0.78). Based on these figures, and taking into account that in the present study more

patients with active cancer will be included, it is expected that the recurrent VTE rate in the apixaban treated patients will not be higher than the 7-8% observed in the LMWH treated groups in CLOT and CATCH studies.

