## 9.7 Handling of data, dropouts and missing values

For the Burden score of ACTS scale, no imputation on missing data will be applied if  $\geq 7$  items are incomplete; otherwise, the Burden score is calculated as the mean of the complete items score x 12. For the Benefit score of ACTS scale, no imputation on missing data will be applied if  $\geq 2$  items are incomplete; otherwise, the Burden score is calculated as the mean of the complete items score x 3.

In the situation where the event date is partial or missing, the date will appear partial or missing in the listings, and any corresponding durations will be presented based on the imputations specified in Section 12 “Partial Date Conventions”.

Other missing data will not be replaced.

The number of patients with missing data will be presented under the “Unknown” category.

Missing values will be included in the denominator count when computing percentages.

When continuous data are being summarized, only the non-missing values will be evaluated for computing summary statistics.

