## **10.8 Analysis of efficacy**

### **10.8.1 Analysis of primary endpoint**

Analyses of the primary efficacy endpoint will be performed using the modified intent-to-treat (mITT) analysis set, the intent-to treat (ITT) analysis set and the per protocol (PP) analysis set.

The mITT and the ITT analyses of the primary endpoint will include endpoints that occur at any time from randomization until the end of the originally intended treatment period regardless of whether subjects were receiving study medication.

The analysis performed on the mITT population will be considered as the primary whereas the analyses performed in the ITT and PP population will be seen as supportive (sensitivity analysis).

The primary efficacy variable, i.e. the time from randomization to the first recurrent thromboembolic event (days), will be analyzed after adjusting estimates for the competing risk of death unrelated to VTE. The competing risk analysis will be performed using the SAS procedure PHREG while the probabilities of failure for the event of interest (first recurrent thromboembolic event) are displayed using cumulative incidence plots which do account for the competing risk (death unrelated to VTE). Patients without recurrent thromboembolic event will be censored at 6- month (i.e. Day 180).

The null hypothesis to be tested will be that apixaban is inferior to dalteparin in the prevention of recurrent thromboembolic events during 6-month follow-up; i.e.  $H_0 \rightarrow E[HR] \geq 2.00$ .

The alternative hypothesis will be that apixaban is non-inferior to dalteparin in the prevention of recurrent thromboembolic events during 6-month follow-up; i.e.  $H_a \rightarrow E[HR] < 2.00$ .

Where:  $E[HR]$  is the Expected (E) apixaban-to-comparator Hazard Ratio (HR), while 2.00 is the prefixed non-inferiority threshold.

The evaluation of the primary objective will be done by considering the time from randomization to the first recurrent thromboembolic event (event of interest) or to the occurrence of death unrelated

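### No planned analysis of the primary endpoint tests the assumed VTE risk after follow-up is lost, and SAP 10.8.1 gives two different censoring rules

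*Protocol*

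**What the plan says.** **Allowance for loss.** Protocol 10.1, its synopsis and SAP 9.3 derive 934 completers and then add: "This sample will be increased to 1168 patients to account for up to 20% lost in total patient-years". They equate this with 40% drop-out spread evenly over six months.

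**Censoring.** The protocol synopsis follows each patient to recurrence, to death unrelated to VTE, "or to the last follow-up if neither a recurrent thromboembolic event nor a competing event occurred within the intended 6-month study treatment period"; Protocol 10.6 has the same rule. SAP 10.8.1 gives two rules. One sentence censors patients without recurrence at six months, defined as Day 180. A later paragraph in the same section censors at last follow-up.

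**Sensitivity analyses.** The mITT analysis is primary. For the rest, SAP 10.8.1 says "the analyses performed in the ITT and PP population will be seen as supportive (sensitivity analysis". By SAP 9.8, the PP set keeps only patients who complete the study in full compliance.

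**Missing data.** SAP 9.7 deals with ACTS items and partial dates, then states: "Other missing data will not be replaced".

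**The concern.** A Fine & Gray model that censors a patient at last contact assumes that, had follow-up continued, the patient would have had the same VTE risk as those still observed in the same arm. Data collected up to that contact cannot check this. The usual safeguard is an analysis that varies the assumption and shows how far it must fail before the conclusion changes.

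The plan has no such analysis. ITT changes who is included but keeps the same censoring. PP removes non-completers, so it says nothing about what happened to them. I found no tipping-point, worst-case, imputation or censoring-weighted analysis of the primary endpoint.

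Treatment is open-label, tablets against daily injections, and the margin rationale (Protocol 10.3, SAP 9.5) itself appeals to possible compliance benefits, so the reasons for leaving could differ by arm. Blinded adjudication protects the classification of events that are reported. It cannot recover events after contact is lost. If lost apixaban patients carried more unseen risk than lost dalteparin patients, the estimated hazard ratio would be too low and non-inferiority too easy to declare.

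**Working it through.** **Inputs from the documents** (Protocol synopsis and 10.1; SAP 9.3): "estimated incidence of the primary efficacy outcome of 7% at 6 months with dalteparin"; "an upper non-inferiority margin of 2.00 for the hazard ratio"; "80% power to show the non-inferiority of apixaban, at a one-sided alpha level of 0.025"; 1:1 allocation. A true HR of 1 is implied by Protocol 10.2, where the apixaban rate "will not be higher than the 7-8% observed in the LMWH treated groups in CLOT and CATCH studies".

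**Step 1: reproduce the plan's figures.**
- Events (Schoenfeld) = 4 × (1.960 + 0.842)² / (ln 2)² = 65.35.
- Completers = 65.35 / 0.07 = 933.5, rounded up to 934.
- Inflated sample = 934 / 0.80 = 1167.5, rounded up to 1168.
- Lost time = 40% drop-out × (3 of 6 months) = 20% of patient-years.

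All agree. With 584 per arm, 584 × 0.07 = 40.9 events are expected per arm. At 20% loss, 32.7 are seen and 8.2 are not.

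**Step 2: false non-inferiority when risk after loss differs.** Let *l* be the share of person-time lost, equal in both arms, and *k* the factor on the apixaban hazard after loss, with dalteparin unchanged. Then
- observed HR = 2.00 / (1 − *l* + *l* × *k*), if the true whole-period HR is 2.00;
- P(false non-inferiority) = Φ( ln(2.00 / observed HR) × √65.35 / 2 − 1.96 ).

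| *l* | *k* | Observed HR | P, 65.35 events | P, arm-specific events |
|---|---|---|---|---|
| any | 1 | 2.00 | 2.5% | 2.5% |
| 5% | 2 | 1.90 | 3.9% | 4.3% |
| 10% | 2 | 1.82 | 5.8% | 6.7% |
| 20% | 2 | 1.67 | 11.1% | 12.8% |
| 20% | 3 | 1.43 | 27% | 31% |

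The last column uses SE = √(1/events on apixaban + 1/events on dalteparin), with 40.9 × (1 − *l*) dalteparin events and that number times the observed HR on apixaban.

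**Step 3: direction.** If *k* is the same in both arms and loss is equal, the factor cancels. If only dalteparin leavers carry double risk at 20% loss, a true HR of 1.00 is observed as 1.20. Power falls to Φ( ln(2/1.20) × √65.35 / 2 − 1.96 ) = Φ(0.10), about 54% instead of 80%.

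**Step 4: what a tipping-point analysis would report.** With the SE taken from observed events, the conclusion changes at *k* = 1 + (2.00/U − 1)/*l*, where U is the upper 95% limit before adjustment. For an observed HR of 1.00 and 20% loss, U = 1.62 and *k* = 1 + 0.232/0.2 = 2.2. Letting imputed events add to the precision gives 2.7.

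| Observed HR | 5% lost | 10% lost | 20% lost |
|---|---|---|---|
| 1.00 | 6.6 to 7.7 | 3.7 to 4.3 | 2.2 to 2.7 |
| 1.20 | 2.8 to 3.2 | 1.8 to 2.1 | 1.24 to 1.56 |

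**Step 5: the Day 180 rule read literally.** A patient lost event-free in month 2 would count as at risk and event-free to Day 180. Under a constant hazard this multiplies the HR by (1 − loss on apixaban)/(1 − loss on dalteparin). The factor is 1 with equal loss. With assumed losses of 30% on apixaban and 10% on dalteparin it is 0.70/0.90 = 0.78; with the losses reversed it is 1.29.

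**The case against.** The strongest reply is that little follow-up may in fact be censored.

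- The documents do not say whether the 20% means loss to follow-up, stopping drug or death. Protocol 10.2 cites six-month mortality of 32% and 40% in the reference trials, so part of the allowance may be death, and non-VTE death is a competing event, not censoring.
- Stopping drug is not censoring either. The mITT and ITT analyses count endpoints on or off drug. Protocol 6.6 follows all randomized patients for seven months, by telephone if needed, and Protocol 6.5.2 counts consent as withdrawn only when four separate methods of follow-up are refused.
- SAP 10.1 already tabulates treatment discontinuation by reason and arm, and SAP 10.8.1 counts censored patients.

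These points stand and they limit the likely size. They do not fill the gap: actual loss is unknown at planning, discontinuation tables do not show patient-days lost to follow-up, and no table tests the assumption.

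Three stronger readings are tempting, and the documents do not support them. A reader might infer that a fifth of follow-up will be censored and that the real error rate is therefore 11% or 27%; but 20% is a planning ceiling, and the hazard multipliers are assumptions found nowhere in the documents. A reader might infer that bias favours apixaban; nothing shows that apixaban leavers are at higher risk, and the burden of injections bears on the dalteparin arm and on stopping drug, which the protocol separates from leaving follow-up. A reader might also infer that all three analyses treat loss as uninformative censoring; PP excludes non-completers instead of censoring them, and the literal Day 180 rule counts their time as event-free.

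**Conclusion.** The point holds as a gap in the sensitivity analyses together with a contradiction in the censoring rule. It is not evidence that the primary result will be biased. The assumption about VTE risk after loss goes untested, and SAP 10.8.1 leaves open which assumption is being made.

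The size depends on how much time is truly censored. With a doubled apixaban hazard after loss, false non-inferiority is about 4% at 5% loss, 6% at 10% and 11% at 20%, against 2.5%. If loss is small and the observed HR is near 1.00, the conclusion would be hard to overturn. If loss approaches the ceiling and the observed HR is near 1.20, a modest difference would be enough.

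These figures assume constant hazards, equal loss in both arms, no centre or stratum covariates, and no modelling of competing deaths. The sample size reproduces and need not change.

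**What to change.** 1. In SAP 10.8.1, state one rule: patients lost alive and event-free before Day 180 are censored at last follow-up, and only those followed to Day 180 are censored at Day 180. This must come first, because under the literal Day 180 rule nobody is censored earlier and there is nothing to impute.
2. Add a pre-specified delta-adjusted tipping-point analysis on the mITT set. For each patient censored alive before Day 180, multiply impute the remaining time to VTE and to competing non-VTE death from arm-specific hazards. Multiply the apixaban VTE hazard by delta (1, 1.5, 2, 3 and upward until the conclusion changes) and keep dalteparin at 1. Refit the Fine & Gray model and report the smallest delta at which the upper 95% limit reaches 2.00. Imputing VTE without competing death would overstate VTE and would not match the primary model.
3. Report patient-days lost to follow-up by arm and reason.

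The cost is some extra programming on data already collected; sample size, margin and visits stay as they are. It should be fixed before results by arm are seen. The downside for the sponsor is that the result may show the conclusion to be fragile.
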